Two Dose Neuraxial Morphine for Prevention of Postdural Puncture Headache

NCT02473276

IRB approval date: 05/12/2023

RESEARCH AIMS & ABSTRACTS

Research Question(s)/Hypothesis(es): This study aims to determine the efficacy of neuraxial (either epidural or intrathecal) preservative-free morphine to prevent headache after accidental dural puncture in parturients.

Our hypothesis is that 2 doses of neuraxial morphine (epidural or intrathecal) will be superior to placebo in reducing the incidence of postdural puncture headache.

Scientific Abstract: Neuraxial analgesia (most commonly continuous epidural or combined spinal epidural) is the most effective modality available for pain relief during labor. Accidental dural puncture (ADP) with a large bore epidural needle and the resulting post-dural puncture headache (PDPH) is one of the most significant sources of anesthesia-related morbidity in parturients. The incidence of ADP in this population is between 0.04 and 6% (most common cited is ~ 1%), and PDPH occurs in up to 80% of patients with an ADP. For many patients, the headache is debilitating, interfering with the ability to care for a new infant, and may be associated with other unpleasant symptoms, including diplopia, tinnitus, hypoacusis, photophobia, nausea, and dizziness. In the most severe cases, subdural hematoma can occur. Epidural blood patch is the gold standard for treatment of PDPH, and although almost always effective, can result in another ADP, as well as low back pain and lower extremity pain. For this reason, effective measures to prevent PDPH when ADP occurs would be highly valuable. One small study by Al-metwalli, et al. in which 50 women were randomly allocated to receive 2 epidural injections of morphine or saline, demonstrated a beneficial effect of epidural morphine in decreasing the incidence of PDPH. This study aims to determine the efficacy of 2 doses of neuraxial (either epidural or intrathecal) preservative-free morphine (PFM) to prevent headache after ADP in parturients.

Lay Abstract: Epidural or combined spinal epidural analgesia (pain relief) is the most effective modality available for the treatment of pain during labor. The most frequent, bothersome complication of performing these procedures is accidental dural puncture (ADP) with the epidural needle, commonly called a “wet tap.” The dura mater is the membrane that surrounds the fluid that cushions and bathes the brain and spinal cord. If the dura mater is

punctured by the epidural needle, some of the fluid may leak out through the puncture. When ADP occurs, the anesthesiologist, at his/her discretion, may either withdraw the needle and place an epidural catheter at the same or slightly different level in the lower back, or the anesthesiologist may decide to place the epidural catheter through the dural puncture directly into the spinal fluid (known as an intrathecal catheter). Following ADP/wet tap, up to 80% of patients get a headache, known as a post-dural puncture headache (PDPH). The headache usually begins 24 – 72 hours after ADP/wet tap occurs. For many patients, the headache is very painful and interferes with care of their newborn. The headache may also be associated with other unpleasant symptoms, including blurry vision, ringing in the ears, muffled hearing, sensitivity to light, nausea, and dizziness. In the most severe and rare cases, bleeding in the brain can occur. Epidural blood patch is the gold standard for treatment of PDPH, and although almost always effective, can result in another ADP, as well as low back pain and lower extremity pain. For this reason, effective measures to prevent PDPH when ADP occurs would be very useful. One recent study in which 50 women were randomly allocated to receive 2 epidural injections of morphine or saline, demonstrated a beneficial effect of epidural morphine in decreasing the incidence of PDPH. This study aims to determine whether administration of 2 doses of morphine, via either the epidural or intrathecal catheter in place, will prevent headache in women who experienced ADP in during labor.

BACKGROUND

Study Purpose and Rationale: Neuraxial (epidural or combined spinal epidural) analgesia is the most effective modality available for pain relief during labor. For obstetric patients who choose to undergo neuraxial analgesia, accidental dural puncture (ADP) with a large bore epidural needle and the resulting post-dural puncture headache (PDPH) is the most significant source of morbidity. The incidence of ADP in this population is between 0.04 and 6%, with most estimates between 1-2% (1), and PDPH occurs in up to 80% of patients with an ADP (2). For many patients, the headache is debilitating, interfering with their ability to care for a new infant, and it may also be associated with other unpleasant symptoms, including diplopia, tinnitus, hypoacusis, photophobia, nausea, and dizziness. In the most severe cases, subdural hematoma can occur. When ADP occurs during the provision of neuraxial labor analgesia,

management includes placement of an intrathecal catheter or placement of an epidural catheter at the same or different intervertebral level. The data that exists is conflicting regarding what techniques or factors may reduce the risk for PDPH. A meta-analysis, which reviewed data from nine studies, found that insertion of an intrathecal catheter produced a significant reduction in the need for epidural blood patch (EBP), although the incidence of PDPH was not significantly different (3). Epidural blood patch (EBP) is the gold standard for treatment of PDPH, and although almost always effective, it is not without the potential for complications. EBP can result in another accidental dural puncture, as well as low back pain and lower extremity pain. For this reason, effective measures to prevent PDPH when ADP occurs would be useful. At the present time, the efficacy of measures such as continuous intrathecal analgesia, intrathecal saline injection, and prophylactic EBP, to prevent PDPH remain unclear.

One small study by Al-metwalli, et al. (4) in which 50 women were randomly allocated to receive epidural injections of morphine or saline, demonstrated a beneficial effect of epidural morphine in decreasing the incidence of PDPH. Interestingly, epidural morphine is often administered for post-operative analgesia after cesarean delivery, and in patients who experience ADP, cesarean delivery is associated with a lower incidence of PDPH than vaginal delivery (5). This study aims to determine the efficacy of neuraxial (either epidural or intrathecal) preservative-free morphine (PFM) to prevent headache after ADP in parturients.

Study Design: This will be a prospective, randomized, double blind clinical trial. Subjects will be postpartum ASA I and II women aged 18 years and older, who are known to have had ADP with an epidural needle during placement of neuraxial labor analgesia, and have either an intrathecal catheter or epidural catheter. Patients will be randomized to either receive PFM or placebo (sterile normal saline). For patients with an epidural catheter, the group “EPID PFM” will receive 3 mg (6 mL) of PFM, followed by 3 mL of sterile normal saline (NS) to be administered through the epidural catheter. The placebo group, “EPID NS”, will receive 6 mL of NS, followed by another 3mL of NS via the epidural catheter. For patients with an epidural catheter, the group “EPID PFM” will receive 3 mg (6 mL) of PFM, followed by 3 mL of sterile normal saline (NS) to be administered through the epidural catheter. The placebo group, “EPID NS”, will receive 6 mL of NS, followed by another 3mL of NS via the epidural catheter. For patients with an intrathecal catheter, the group, “IT PFM” will receive 200 micrograms (mcg)

(0.4 mL) of preservative-free morphine, followed by a flush of the catheter with 2 mL of NS. The placebo group, IT SAL will receive 0.4 mL and then 2 mL of NS through the intrathecal catheter. 16 to 24 hours after receiving the first study drug, patients in all groups will be visited by an investigator, and then daily thereafter during the hospital admission. They will be evaluated for the presence of headache, analgesia requirements, need for EBP and the severity of opioid side effects. As long as the patient is afebrile, has not been experiencing severe opioid side effects and the catheter is in place and intact, the patient will then receive the identical study drug (for a total of two doses). The epidural/intrathecal catheter will be removed immediately after the second administration of the study drug. After discharge, the patient will be followed up once daily by telephone for up to a minimum of 5 days after receiving the last dose of the study drug if they remain headache free, and for a minimum of 3 days after resolution of PDPH.

Statistical Procedures: This will be a prospective randomized double blind clinical trial. The primary outcome of the trial will be the incidence of PDPH at 48 hours after ADP. A study by Al-Metwalli et al. 2008 (4), utilizing 2 doses of epidural morphine, reported a PDPH headache rate of 12 % in the treatment arm and 48% in the saline arm. Estimates of PDPH rate after ADP range from 50 - 85%. Our internal QA data indicates our PDPH headache rate after an ADP with an epidural needle over the past several years is ~66%. We will consider a difference in incidence of PDPH between the placebo and treatment groups of 25% to be significant, based on the findings of Al Metwalli et al. (4) and the meta-analysis by Heesen et al. (3). For calculation of our sample size, we determined that an absolute 25% decrease in PDPH would be clinically significant (i.e., 66% - 40%). For a power of 90% and an alpha of 0.05%, this requires 83 subjects per group (2 epidural groups compared to each other, 2 spinal groups compared to each other). We are not specifically powering this for comparison of the spinal to the epidural groups, although we will likely be able to do so. We therefore aim to recruit 100 subjects per group (for a total of 400 across all centers) assuming 10- 15% of subjects may be lost because of inadvertent withdrawal of the catheter, subject withdrawal or loss to follow up after discharge. This is intended to be a multicenter study involving 5 or more academic tertiary-care hospitals, having >2,000 vaginal deliveries per year. Since the rate of accidental dural puncture is between 1 and 2%, we estimate we should be able to recruit 100 patients per year. Categorical data (presence of absence of PDPH, need for EBP) will be analyzed using Chi-square analysis. The

two main campuses of NYP will be included (CUMC (including Allen) and Weill-Cornell); additional centers will be enrolled.

REFERENCES

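### Eligibility does not limit delivery mode and nothing governs non-study neuraxial morphine, so placebo women delivered by caesarean could receive the test drug class and dilute the effect

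*Combined protocol and SAP*

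**What the plan says.** The population is defined in Study Design: "Subjects will be postpartum ASA I and II women aged 18 years and older, who are known to have had ADP with an epidural needle". The puncture must have happened while labour analgesia was being placed, and the woman must "have either an intrathecal catheter or epidural catheter". Delivery mode is not a criterion.

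The end of Study Purpose and Rationale, just before Study Design, makes two statements about caesarean delivery. One is that "epidural morphine is often administered for post-operative analgesia after cesarean delivery". The other is that, among women with accidental dural puncture, "cesarean delivery is associated with a lower incidence of PDPH than vaginal delivery". Both are offered as support for the hypothesis that neuraxial morphine prevents PDPH.

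Statistical Procedures mentions delivery mode once, when it describes participating hospitals as "having >2,000 vaginal deliveries per year". The presence of PDPH and the need for blood patch "will be analyzed using Chi-square analysis", separately for the epidural and the intrathecal pair of groups. There is no stratification or adjustment by delivery mode. The sample size is 83 per group for 90% power to detect 66% versus 40%, raised to 100 per group for 10–15% loss.

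Study Design has an investigator assess analgesia requirements at 16 to 24 hours and daily in hospital. It does not say whether this covers neuraxial morphine given outside the study, or how the information would be used.

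**The concern.** The document names a group that often receives the test drug class as routine care and leaves that group eligible for a saline control. If a placebo woman receives clinical neuraxial morphine, and morphine works as the trial supposes, her risk moves toward that of the active arm. The expected difference shrinks however well the arms are balanced, and power falls below the stated 90%. The sample size makes no allowance for this. Without a specific record of non-study neuraxial morphine, a small or null difference would be hard to interpret afterwards.

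**Working it through.** **Inputs from Statistical Procedures.** Control rate 66%, treated rate 40%, power 90%, 83 per group, equal groups. Alpha is printed as 0.05%. I use two-sided 0.05 because it reproduces 83; a literal 0.0005 would need 165 per group even without continuity correction. Sidedness is not stated.

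**Assumed input.** f is the share of placebo women who receive clinical neuraxial morphine with the full planned effect. The document gives neither a caesarean share nor a rate of morphine use, so f is shown over a range.

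**Step 1: reproduce 83.** With pc = 0.66, pt = 0.40, d = 0.26 and mean rate p = 0.53:

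n0 = [1.96·√(2p(1−p)) + 1.2816·√(pc(1−pc) + pt(1−pt))]² / d²
= [1.96 × 0.7058 + 1.2816 × 0.6815]² / 0.0676 = 75.3, so 76 per group.

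With continuity correction, n = (n0/4)·[1 + √(1 + 4/(n0·d))]² = 82.9, so 83. The plan's figure is the corrected one, and it assumes no morphine in the placebo arm.

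**Step 2: dilute the control rate.** pc(f) = 0.66 − 0.26f, with the morphine arm held at 0.40.

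**Step 3: power at 83 per group.** Power = Φ{[d − 1/83 − 1.96·√(2p(1−p)/83)] / √([pc(1−pc) + pt(1−pt)]/83)}. The uncorrected version drops the 1/83. At f = 20%, pc = 0.608 and d = 0.208, so (0.208 − 0.0120 − 1.96 × 0.0776)/0.0759 = 0.577, and power is 72%.

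| f | Difference (points) | Power at 83, corrected | Power at 83, uncorrected | n per group for 90%, corrected | n per group for 90%, uncorrected |
|---|---|---|---|---|---|
| 0% | 26.0 | 90% | 93% | 83 | 76 |
| 10% | 23.4 | 82% | 86% | 103 | 94 |
| 20% | 20.8 | 72% | 77% | 129 | 120 |
| 30% | 18.2 | 59% | 65% | 168 | 157 |

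**Step 4: how far this is an upper bound.** f is the caesarean share times the proportion of those women given neuraxial morphine. If half of them receive it, or if it has half the planned effect, 0.26f is halved. A 20% share then behaves like the 10% row.

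**Step 5: what if 66% already includes caesarean women?** The plan does not split that rate by delivery mode. Hold the control arm at 66% and let a share f of women contribute no contrast, so that the treated rate is 0.66 − 0.26(1 − f). Corrected power at 83 is then about 83%, 72% and 60% for f = 10%, 20% and 30%. The loss is almost the same.

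**Step 6: does the recruitment margin absorb it?** Only if nobody is lost. With all 100 per group evaluable, corrected power is 89%, 80% and 68% at f = 10%, 20% and 30%. The margin is already committed to dropout: 83/0.85 = 97.6, so 98.

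**Step 7: does the plan's forecast depend on caesarean women?** Its stated minimum figures give 5 hospitals × 2,000 vaginal deliveries × 1% = 100 women per year, which is the forecast.

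**The case against.** The best reply is that the plan probably means vaginal deliveries. Sites and recruitment are expressed in vaginal deliveries, no sentence says that caesarean women are to be enrolled, and the remark on post-caesarean morphine describes general practice, not care within this trial. This stands in part. Caesarean women are eligible by silence, and contamination is an inference. A reader might conclude that the sponsor chose to enrol caesarean women, or that placebo women will receive morphine. The document supports neither; it supports only that both are possible under the text as written. The line on vaginal deliveries describes hospitals, however, and does not restrict subjects.

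The power figures also take a full-effect case. Often does not mean always, and nothing equates routine postoperative morphine with the two-dose study regimen. That stands, and is why the figures are given as an upper bound for each assumed share.

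A reader might also infer that leaving delivery mode out of the chi-square biases the result, or that it is a strong prognostic factor. Neither follows. The document gives a direction and no size, randomisation balances delivery mode in expectation, and chance imbalance is ordinary sampling error that the test already allows for.

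Nor is it established that a null result would be beyond interpretation, since analgesia requirements are assessed in hospital. The gap is that capture of non-study neuraxial morphine, and its use in the analysis, are not specified.

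**Conclusion.** The point holds as a gap in eligibility and in the handling of non-study neuraxial morphine. Followed as written, the plan can admit placebo women who receive the test drug class, and its 90% power assumes that none do. If 10–30% of placebo women did so with the full planned effect, corrected power at 83 per group would be about 82% down to 59% (86% down to 65% uncorrected). The loss is smaller if fewer women receive it or its effect is weaker. These figures rest on an assumed share, on morphine working as hypothesised, and on an unchanged 40% in the morphine arm.

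Sample sizes must be compared within one formula. Setting the uncorrected 120 at f = 20% against the plan's 83 would understate the increase; the like-for-like pairs are 129 versus 83, or 120 versus 76. This should be settled in the plan, but it does not show that the trial is biased or that contamination occurred.

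**What to change.** **Preferred.** Add vaginal delivery to the eligibility sentence in Study Design. Subjects are postpartum, so delivery mode is known before randomisation and the restriction cannot bias the comparison. It matches the basis of the plan's recruitment forecast. The cost is one line, some women not enrolled, and results that apply to vaginal delivery only.

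**If caesarean women are to stay eligible:**
- Stratify randomisation by delivery mode.
- Record all neuraxial morphine given outside the study.
- Replace the plain chi-square with a Mantel-Haenszel comparison stratified by delivery mode, within each catheter type.
- Report the vaginal-delivery result as supportive. It should not be the deciding estimate: at a 20% caesarean share, 0.8 × 83 leaves about 66 per group, with 81% power (corrected) or 86% (uncorrected) for 66% versus 40%.
- State that the 90% power assumes no non-study neuraxial morphine in the placebo arm. Stratified analysis does not restore a diluted contrast.

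This costs one stratification factor, one recorded variable and two sentences in Statistical Procedures.

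Either way, the sponsor should reconcile the eligibility sentence with the Background statement on routine post-caesarean morphine. No clinical analgesia rule is proposed here.

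### A headache that began before the first dose can be enrolled and counted as a primary event, which dilutes a prevention trial by a probably modest amount

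*Combined protocol and SAP*

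**What the plan says.** The aim, under Research Question(s)/Hypothesis(es), is "to determine the efficacy of neuraxial (either epidural or intrathecal) preservative-free morphine to prevent headache after accidental dural puncture in parturients".

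The Study Design section sets eligibility in one sentence: "Subjects will be postpartum ASA I and II women aged 18 years and older, who are known to have had ADP with an epidural needle". The puncture must have happened when labor analgesia was being set up, and the sentence closes with a catheter requirement: "and have either an intrathecal catheter or epidural catheter". Headache status is not among the conditions.

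The first headache evaluation described is after dosing: "16 to 24 hours after receiving the first study drug, patients in all groups will be visited by an investigator", with daily visits after that. The second dose depends on three things: "As long as the patient is afebrile, has not been experiencing severe opioid side effects and the catheter is in place and intact". Headache status is not one of them either.

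Under Statistical Procedures, "The primary outcome of the trial will be the incidence of PDPH at 48 hours after ADP". The Lay Abstract adds a fact that bears on timing: "The headache usually begins 24 – 72 hours after ADP/wet tap occurs".

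**The concern.** The puncture happens when labor analgesia is placed, and study drug starts postpartum. Labor and delivery lie between the two, and the plan puts no upper limit on that interval. The outcome clock runs from the puncture, so it is already running when a woman is randomised. A woman whose headache started in the interval meets every stated entry condition and, if the headache is there at 48 hours, meets the primary outcome as well.

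No study drug can prevent a headache that has already begun. Such events are expected at the same rate in both arms, so they add to both event rates and shrink the difference between them. What is at stake is power, and an estimate that understates the preventive effect. The plan describes no record from which the size of this dilution could be judged.

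**Working it through.** **Inputs.** From Statistical Procedures: PDPH 66% on placebo and 40% on morphine, 90% power, 83 per group, 100 per group recruited, 10–15% loss. Alpha is printed as 0.05%; I read it as 0.05, two-sided, because only that reproduces the plan's number. The share e of randomised women who already have PDPH at dose 1 is not in the documents, so it is an assumption, shown as a range.

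**The plan's own figure.** With p1 = 0.66, p2 = 0.40 and mean p̄ = 0.53:

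n₀ = [1.960·√(2·p̄(1−p̄)) + 1.282·√(p1(1−p1) + p2(1−p2))]² / (p1−p2)² = 75.3, so 76.

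With continuity correction, n = (n₀/4)·[1 + √(1 + 4/(n₀·0.26))]² = 82.9, so 83. The stated 83 reproduces exactly. The calculation is sound; it makes no allowance for headaches present before dose 1.

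**Power formula** (two-sided 5%, no continuity correction):

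power = Φ[(p1−p2 − 1.960·se₀)/se₁], where se₀ = √(2p̄(1−p̄)/n) and se₁ = √((p1(1−p1) + p2(1−p2))/n).

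**Two scenarios**, because the plan does not say whether its 66% includes early headaches.

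- A: the 66% includes them, and the planned relative effect (40/66) applies only to the rest. Then p1 = 0.66 and p2 = e + (0.66−e)·(0.40/0.66).
- B: 66% against 40% applies to women free of headache at dose 1. Then p1 = e + (1−e)·0.66 and p2 = e + (1−e)·0.40.

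Example, A with e = 5%: p2 = 0.05 + 0.61 × 0.6061 = 0.4197, difference 0.2403, se₀ = 0.0774, se₁ = 0.0751. Power = Φ[(0.2403 − 0.1516)/0.0751] = Φ(1.18) = 88.1%.

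| e | A: difference | A: power at 83 | A: n for 90% | B: difference | B: power at 83 | B: n for 90% |
|---|---|---|---|---|---|---|
| 0 | 26.0 | 92.6% | 83 | 26.0 | 92.6% | 83 |
| 2% | 25.2 | 91.0% | 88 | 25.5 | 91.6% | 86 |
| 5% | 24.0 | 88.1% | 97 | 24.7 | 90.0% | 91 |
| 10% | 22.1 | 82.1% | 114 | 23.4 | 86.9% | 100 |

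Differences are in percentage points. The n columns are per group with continuity correction, as in the plan's own figure. The power columns are uncorrected, which is why the starting value is 92.6% and not 90%.

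**Effect of the recruitment margin.** With 100 recruited and 10–15% lost, 85 to 90 per group remain. At e = 5%, power is then 88.9–90.5% under A and 90.7–92.2% under B. At e = 10% it is 83.0–85.1% under A and 87.7–89.5% under B.

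**How large e might be.** Under A, e = 10% means that 0.10/0.66 = 15% of placebo headaches start before dose 1; e = 5% means 7.6%, and e = 2% means 3.0%. With usual onset at 24–72 hours after ADP, the larger values need a long interval between puncture and dose 1. The plan does not state that interval.

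**The case against.** The point rests on silence. No sentence says that women with a headache are to be enrolled. The words prevent and incidence, and the follow-up rule for women who stay headache-free, all suggest that new headaches were meant. This is fair and limits confidence. It also means that the fix would only write down the likely intent, which matters when 5 or more hospitals must apply the same rule.

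The usual onset of 24–72 hours suggests few affected women if dose 1 comes soon after the puncture, and at small e the loss is slight. This stands. The reply is only that the interval is neither limited nor recorded.

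The phrase at 48 hours can be read as status at that time, in which case an early headache that had resolved would not count. This is open in the text. It would remove some pre-dose cases, but not those still present at 48 hours.

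Three stronger readings are tempting, and the documents support none of them:

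- A reader might infer bias towards morphine or a raised false-positive rate. Pre-dose events are equally likely in both arms under randomisation, and a chance imbalance in them is ordinary sampling error that the Chi-square test already covers.
- A reader might infer that pre-dose cases could never be separated afterwards. Women are asked about headache at the 16–24 hour visit, and onset time could be asked then; the plan simply does not describe recording it.
- A reader might take a power of 82% as the expected result. It belongs to the less favourable scenario at an assumed e of 10%.

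**Conclusion.** The point holds as a gap between the entry criteria, the start of treatment and the outcome clock. As written, a PDPH that began before dose 1 can be enrolled and counted, and the consequence is dilution towards no difference. The loss of power at 83 per group is 1 to 2 points at e = 2%, about 3 to 4 at e = 5% and about 6 to 10 at e = 10%. These figures assume equal e in both arms, no effect of morphine on a headache already present, and the planned effect in all other women. The true e cannot be derived from the documents and is probably small if dose 1 follows the puncture closely.

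Severity is minor to moderate and confidence is moderate. The trial remains interpretable without the change, but any dilution would be avoidable and, as the plan stands, unmeasured.

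**What to change.** 1. Add to eligibility in Study Design: no postural headache or suspected PDPH at randomisation. This is narrower than excluding any headache.
2. Randomise immediately before dose 1, and record headache status and time since ADP at dose 1.
3. In Statistical Procedures, define the primary event as PDPH with onset after randomisation and by 48 hours after ADP.
4. Keep all randomised women in the primary analysis. Count a headache that starts between randomisation and dose 1 as an event, and add a sensitivity analysis without those women.

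The cost is one eligibility line, one bedside question and one timestamp per woman. Some women with an early headache would not be enrolled. The control rate may also fall slightly below 66%: under scenario A with e = 5%, it would be (0.66 − 0.05)/0.95 = 64.2%. The sample-size paragraph should state which population its 66% describes.

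### The primary outcome closes 48 h after puncture while dose 2 is timed from a postpartum dose 1, so little or none of the window may follow the second dose

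*Combined protocol and SAP*

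**What the plan says.** The combined protocol and SAP uses two different clocks.

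- **Intervention.** Research Question(s)/Hypothesis(es): "Our hypothesis is that 2 doses of neuraxial morphine (epidural or intrathecal) will be superior to placebo".
- **Puncture and treatment.** Study Design enrols women "known to have had ADP with an epidural needle during placement of neuraxial labor analgesia", so the puncture comes before delivery. The same sentence begins "Subjects will be postpartum ASA I and II women aged 18 years and older", so labour and delivery lie between puncture and dose 1. No section gives that interval or limits it.
- **Second dose.** Study Design: "16 to 24 hours after receiving the first study drug, patients in all groups will be visited by an investigator". If the woman has no fever, no severe opioid side effects and an intact catheter, "the patient will then receive the identical study drug (for a total of two doses").
- **Primary outcome.** Statistical Procedures: "The primary outcome of the trial will be the incidence of PDPH at 48 hours after ADP". Nothing elsewhere ties it to either dose.
- **Onset and follow-up.** Lay Abstract: "The headache usually begins 24 – 72 hours after ADP/wet tap occurs". Study Design has daily contacts, after discharge by telephone, for a "minimum of 5 days after receiving the last dose of the study drug if they remain headache free".

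**The concern.** Treatment is timed from dose 1 and the outcome from the puncture. The time that a woman's primary outcome has to reflect the second dose therefore depends on how long after puncture she was first dosed. With a short interval, much of a day remains. With a long one, the outcome closes within hours of dose 2 or before it, and she contributes a one-dose result to a test of a two-dose course.

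The stated onset range adds weight. Headaches that begin between 48 and 72 h after puncture are ones that dose 2 might prevent, and the primary outcome does not count them. At stake is how much of the course's effect the primary analysis can detect, and how clearly a negative result could be read.

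**Working it through.** **The plan's own figure.** Statistical Procedures asks for 83 women per group for 66% against 40% at 90% power. Take alpha as 0.05 two-sided (it is printed as 0.05%, and sidedness is not stated) and mean rate (0.66 + 0.40)/2 = 0.53:

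n = [1.960 × √(2 × 0.53 × 0.47) + 1.282 × √(0.66 × 0.34 + 0.40 × 0.60)]² / 0.26², which rounds up to 76, or 83 with the continuity correction.

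The sample size reproduces and is not in dispute.

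**Timing.** Inputs:

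- T = hours from puncture to dose 1 (not in the documents; a range is shown)
- dose 1 to dose 2 = 16 to 24 h (Study Design, reading dose 2 as given at that visit)
- outcome closes at 48 h after puncture (Statistical Procedures)

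Dose 2 falls at T + 16 to T + 24 h after puncture. Time left in the window is 48 − (T + 24) to 48 − (T + 16), that is 24 − T to 32 − T hours.

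| T (h) | Dose 2, h after puncture | Hours left in primary window |
|---|---|---|
| 4 | 20 to 28 | 20 to 28 |
| 8 | 24 to 32 | 16 to 24 |
| 12 | 28 to 36 | 12 to 20 |
| 18 | 34 to 42 | 6 to 14 |
| 24 | 40 to 48 | 0 to 8 |
| 28 | 44 to 52 | none to 4 |
| 32 | 48 to 56 | none |

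From T = 24 the window can close by the time of dose 2 (with the 24 h interval). From T = 32 it always does, even with the 16 h interval. Whether incidence at 48 h means cumulative to 48 h or present at 48 h, it closes at the same time.

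**Illustration of size (assumed shares, not from the documents).** Suppose a fraction f of women keep only a fraction k of the benefit by 48 h. The morphine rate becomes 0.66 − 0.26 × [1 − f(1 − k)]. Power at 83 per group, two-sided 0.05, no continuity correction:

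| f | k | Morphine rate | Power |
|---|---|---|---|
| 0 | any | 40.0% | 92.6% |
| 10% | 0.5 | 41.3% | 89.8% |
| 10% | 0 | 42.6% | 86.4% |
| 20% | 0.5 | 42.6% | 86.4% |
| 20% | 0 | 45.2% | 77.4% |

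The k = 0 rows assume that dose 1 alone does nothing by 48 h, which is the pessimistic end. If dose 1 delivers the full benefit, nothing is lost.

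**Alternative window.** Closing at 72 h after dose 1 leaves 72 − 24 = 48 to 72 − 16 = 56 h after an on-schedule dose 2, whatever T is. In hours from puncture it closes at T + 72, so it always passes the 72 h end of the stated onset range. Follow-up of headache-free women for at least 5 × 24 = 120 h after the last dose covers it, including in women who receive only dose 1.

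**The case against.** The strongest reply is that the size is undocumented. Nothing says that women are dosed 24 h or more after puncture, and at T = 8 the plan leaves 16 to 24 h after dose 2. This stands: neither the share affected nor the loss of power can be computed, and the power table only illustrates. But the plan neither limits T nor provides for recording it, so it cannot show that the problem is small.

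Stronger readings that a reader might infer do not hold:

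- *The comparison is biased.* It is not. Allocation is random, so T is balanced in expectation, and the 48 h result remains a fair test of assignment to the course on the stated outcome.
- *A null result could not be read at all.* This goes too far. It would be a valid null for PDPH by 48 h after puncture, but possible dilution makes it harder to interpret.
- *The window stops a positive result being credited to the second dose.* The window is not the cause. There is no one-dose arm, so no window separates dose 2 from dose 1.
- *Labour length alone decides who is tested on two doses.* Dose 2 also depends on fever, side effects and the catheter, and Statistical Procedures expects some catheters to be lost. That mix belongs to the planned regimen and would remain under any window.

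Later headaches would be seen in the daily contacts, as the other side can say. They would not enter the primary outcome. It is also fair that a window starting at dose 1 needs a rule for headaches already present by then, and a check on the planning rates.

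**Conclusion.** The point holds as a mismatch between the outcome's time origin and the course under test. Only 24 − T to 32 − T hours of the primary window follow dose 2, falling to none at T = 32 or more. This rests on reading dose 2 as given at the 16 to 24 h visit; a later dose 2 would leave less time. The consequence is under-capture of any benefit from dose 2, of unknown size, and a null result that is harder to interpret. It should be corrected because the outcome rule, followed exactly, can close before or soon after the second dose that the hypothesis names.

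**What to change.** Reconcile the two clocks by changing the outcome, not the dosing:

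1. Define the primary outcome as PDPH with onset from dose 1 to a fixed time that covers the planned course, for example 72 h after dose 1, in all randomised women whether or not they receive dose 2. Restricting to women who received dose 2 would select on events after randomisation.
2. State one rule, the same in both arms, for headaches that begin before dose 1. These matter most when T is long, since usual onset is given as starting 24 h after puncture.
3. Record the time from puncture to dose 1 and report its distribution by arm.
4. Confirm that 66% and 40% are suitable rates for the new window. The internal figure of about 66% is quoted without a 48 h limit, so it may carry over, but the plan should say so.
5. Keep PDPH at 48 h after puncture as a secondary outcome.

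The cost is protocol wording, one recorded time and a check of the planning rates; no contacts are added. The downside is that the primary figure is less directly comparable with rates counted from puncture, which the secondary outcome partly offsets.
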